- Participant meets study definition of SLE, MS, RA, IBD, PsO/PsA, SOT, SCT, HM, ST, or HIV (see Appendix A: ICD-10-CM Codes for IC and Appendix B: Validated Coding Algorithms for IC conditions). Codes for IC conditions will be identified in the health plan claims of the DRN during the period 273 days prior to the pregnancy start date through the first trimester (98 days after the pregnancy start date). Diagnoses recorded through the first trimester will be included to account for women who may not have frequent visits prior to pregnancy and may have a more complete assessment of medical conditions during the first prenatal care visit.
- Participant has at least 273 days of continuous health plan enrollment with medical and drug benefits prior to the start of pregnancy through the delivery date, with gaps of up to 45 days in coverage being permitted. The 273-day pre-pregnancy period through the first trimester (a period of 98 days after the pregnancy start date) was chosen to allow identification of potential confounders of interest (Section 9.3.3). In Sentinel projects, gaps of 45 days or less in health plan enrolment are

214420 (EPI-ZOSTER-039 VS US DB) Protocol Amendment 2 Final

typically considered administrative gaps (and not lapses in health plan coverage) and ignored.

Pregnancies will be excluded from the study if the following exclusion criterion is met:

- Participant was exposed to a medication(s) that presents a known increased risk for fetal malformations (see Appendix C: Teratogenic and Fetotoxic Medications)
- Participant delivered an infant identified as having a chromosomal or genetic anomaly (Appendix D: Diagnosis Codes for Chromosomal or Genetic Anomalies
- Ectopic pregnancies, molar pregnancies or induced abortions.
- Multigestation (e.g., twin) pregnancies.

For analyses evaluating infant outcomes (Primary Objective and Secondary Objective 1), the cohort will include pregnancies resulting in live births for which the mother is linked to an infant. Each Sentinel Data Partner will be responsible for linking mothers to infants using all available local data resources. Algorithms linking mothers to infants will vary across Data Partners, generally looking for equivalent health plan subscriber numbers, delivery dates and dates of birth, and shared names and addresses. Sentinel Data Partners are able to link approximately 74% of their infants to their mothers [Sentinel Initiative, 2018].

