9.3.3. Other Variables (Amended 15 August 2022)

The propensity score reflects the conditional probability of a woman being exposed to HZ/su during pregnancy given baseline potential confounders. Potential confounders to be used in the estimation of the propensity score will be identified in the *273* days prior to the pregnancy start date through the first trimester (period 98 days after the pregnancy start date). This baseline period was selected to provide an adequate covariate evaluation window to capture diagnoses/encounters for most chronic conditions in the health plan

214420 (EPI-ZOSTER-039 VS US DB) Protocol Amendment 2 Final

claims. Diagnoses recorded through the first trimester will be included to account for women who may not have frequent visits prior to pregnancy and may have a more complete assessment of medical conditions during the first prenatal care visit. Separate propensity score models will be fit for the cohorts of eligible live birth pregnancies and cohorts of all eligible pregnancies. Information about variables that may predict the likelihood of exposure will be collected from health plan claims data. These variables will include maternal age, calendar year, maternal comorbidities (Appendix I:. Maternal Comorbidities), tobacco use, alcohol use, drug dependence, maternal obesity, and maternal race/ethnicity, and U.S. region of residence (Midwest, West, South, Northeast). In addition, the number of healthcare encounters (outpatient, emergency department, inpatient) in the 273 days preceding the pregnancy start date will be identified.

The propensity score model will be fit separately for each DP and matching on the propensity score will occur within DP. The propensity score will be calculated by each DP using logistic regression. The main reason to use DP-specific propensity score is to protect sensitive individual and institutional information. It is also desirable to generate and match propensity scores within DP and match within DP because DP can be representative of background variables at the DP level (e.g., insurance coverage), which will not be available at individual level. The large number of enrollees of each DP is additional assurance that the best control will be within DP. Further description of the analytical steps of the data is provided in the SAP.

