Appendix B. Validated coding algorithms for IC conditions (Amended 15 August 2022)

We will use the validated algorithms in the CBER Biologics Effectiveness and Safety (BEST) Initiative report [Saunders-Hastings, 2021] to identify IC conditions (solid organ transplant [SOT], stem cell transplant [SCT], hematological malignancy [HM], solid tumor [ST], human immunodeficiency virus [HIV]), as these are specific to each IC condition as well as valid and consistent with the typical approaches that are used in Sentinel. Algorithms for the IC conditions are described below:

- 1) HIV/AIDS: ≥ 2 claims for ANY HIV/AIDS diagnostic or procedural codes. a. This category is viewed as immunocompromised regardless of treatment status (treatment [RX]-independent)
- b. EXCLUDE cases where the most recent claim is MORE THAN 6 months prior to the index date.
- 2) Hematologic Malignancy and Related Conditions: ≥ 2 claims for ANY relevant diagnostic codes. a. This category is viewed as immunocompromised regardless of treatment status (RX-independent).
- b. EXCLUDE cases where the most recent claim is MORE THAN 6 months prior to the index date.
- 3) Solid Malignancy: ≥ 2 claims for ANY solid malignancy diagnostic codes AND one of: a. ≥ 2 claims for ANY codes for chemotherapy or radiation
- b. ≥ 2 claims for ANY codes for immune-modulating or immunosuppressant therapy
- c. EXCLUDE cases where the most recent claim is MORE THAN 6 months prior to the index date.

NOTE: Codes for brachytherapy may also be considered by users seeking to apply a more inclusive definition of radiation therapy. It is recommended that this category be ignored in regular applications of the algorithm, but it may be of value to those with a specific interest in brachytherapy.

- 4) Transplant and Related Conditions: ≥ 1 claims for ANY transplant or related condition diagnostic codes AND one of: a. ≥ 2 claims for ANY codes for chemotherapy or radiation
- b. ≥ 2 claims for ANY codes for immune-modulating or immunosuppressant therapy
- c. EXCLUDE cases where the most recent claim is MORE THAN 6 months prior to the index date.

NOTE: Codes for brachytherapy may also be considered by users seeking to apply a more inclusive definition of radiation therapy. It is recommended that this category be ignored in regular applications of the algorithm, but it may be of value to those with a specific interest in brachytherapy.

214420 (EPI-ZOSTER-039 VS US DB) Protocol Amendment 2 Final

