For autoimmune diseases (AIDs) (systemic lupus erythematosus [SLE], multiple sclerosis [MS], rheumatoid arthritis [RA], inflammatory bowel disease [IBD], psoriasis [PsO], and psoriatric arthritis [PsA]), we prefer to use other coding algorithms from the literature that are AID-specific instead of the coding algorithms in the CBER Biologics Effectiveness and Safety (BEST) Initiative assessment report [Saunders-Hastings, 2021], as the algorithms that are presented in this report are not AID-specific. We will use algorithms that are valid and consistent with the typical approaches that are used in Sentinel as described below.

SLE

- ≥1 rheumatologist diagnosis code for SLE (ICD-10 M32.1, M32.8, M32.9) in the 365-day baseline period prior to the index date.
 - The above algorithm has demonstrated a PPV of 95% and sensitivity of 83% [Hanly, 2014].

MS

- \geq 3 of any combination of inpatient diagnoses (any position) of MS (ICD-10 G35), ambulatory visit (AV) diagnoses of MS, emergency department (ED) diagnoses of MS, and MS-specific disease-modifying therapy fills/infusions during the 365-day baseline period. At least one of these must be an inpatient, AV, or ED diagnosis of MS.
 - This algorithm has demonstrated a PPV of 95-97% and sensitivity of 85-93% [Culpepper, 2019].

RA

- \geq 1 inpatient claim with a diagnosis code for RA (ICD-10 M05, M06) OR \geq 2 physician outpatient claims with RA diagnosis during an office visit and/or emergency visit that are at least 30 days apart in the 365-day baseline period prior to the index date
 - The above algorithm has no demonstrated PPV but has been used extensively in the literature [MacLean, 2000].

IBD

- \geq 1 inpatient claim with a diagnosis code for IBD (ICD-10 K50, K51) OR \geq 2 physician outpatient claims with IBD diagnosis during an office visit and/or emergency visit that were at least 30 days apart in the 365-day baseline period prior to the index date [Weng, 2007]
 - The above algorithm has no demonstrated PPV but has been used extensively in the literature [Weng, 2007].

PsO

- ≥1 dermatologist diagnosis code for PsO (ICD-10 L40) in the 365-day baseline period prior to the index date.
 - The above algorithm has demonstrated a PPV of 90% and sensitivity of 88% [Asgari, 2013]. This algorithm assumes PsO without PsA.

214420 (EPI-ZOSTER-039 VS US DB) Protocol Amendment 2 Final

PsA

- ≥2 rheumatologist diagnosis code for PsA (ICD-10 L40.5) in the 365-day baseline period prior to the index date.

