Appendix C. Teratogenic and Fetotoxic Medications (Amended 15 August 2022)

Women exposed to any of following potentially teratogenic or fetotoxic medications in the **273** days prior to and during pregnancy will be excluded from the study population. Exposures will be identified from NDC or HCPCS codes in the health plan claims data (outpatient pharmacy dispensing and encounter files).

Drug Class	Drug Name
Vitamin A Analog	Isotretinoin
Vitamin A Analog	Bexarotene
Vitamin A Analog	Acitretin
Prostaglandin Analog	Misoprostol
Antineoplastic	Methotrexate
Immunosuppressant	Mycophenolate Mofetil
Immunologic	Azathioprine
Immunologic	Thalidomide
Anticoagulant	Warfarin
Mood Stabilizer	Lithium
Antiarrhythmic	Amiodarone
Antiarrhythmic	Dronedarone
Anticonvulsant	Carbamazepine
Anticonvulsant	Fosphenytoin
Anticonvulsant	Mephobarbital
Anticonvulsant	Phenobarbital
Anticonvulsant	Phenytoin (phenytoin sodium)
Anticonvulsant	Primidone Primidone
Anticonvulsant	Topiramate
Anticonvulsant	Valproic Acid and derivatives (valproate sodium, divalproex)
Antirheumatic	Leflunomide
ACE-I	Benazepril
ACE-I	Captopril
ACE-I	Enalapril
ACE-I	Fosinopril
ACE-I	Lisinopril
ACE-I	Moexipril
ACE-I	Perindopril
ACE-I	Quinapril
ACE-I	Ramipril
ACE-I	Trandolapril
ARB	Candesartan
ARB	Eprosartan
ARB	Irbesartan
ARB	Losartan
ARB	Olmesartan
ARB	Telmisartan
ARB	Valsartan
Misc Antihypertensive	Aliskiren
SSRI	Paroxetine
Antiinfectives	Trimethoprim
Antiinfectives	Trimetrexate

ACE-I = Angiotensin-converting enzyme inhibitor; ARB = angiotensin II receptor blockers; SSRI = selective serotonin reuptake inhibitor

214420 (EPI-ZOSTER-039 VS US DB) Protocol Amendment 2 Final

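### Appendix C's closed list names one product each for mycophenolate and leflunomide, so pregnancies exposed to other products of the same active substances would stay in the primary malformation analysis

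*Protocol*

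**What the plan says.** The exclusion criterion in Section 9.2.1 is broad: "Participant was exposed to a medication(s) that presents a known increased risk for fetal malformations". It is defined by reference to Appendix C.

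Appendix C then narrows it to a fixed table of drug names: "Women exposed to any of following potentially teratogenic or fetotoxic medications in the" 273 days before and during pregnancy are excluded. The search method is stated as well: "Exposures will be identified from NDC or HCPCS codes in the health plan claims data".

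In that table, valproate is entered with its other forms, "Valproic Acid and derivatives (valproate sodium, divalproex". Phenytoin is entered with its sodium salt, and fosphenytoin has its own line. For the two drugs at issue there is one product each: "Mycophenolate Mofetil" and leflunomide.

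Section 9.2.1 makes multiple sclerosis, lupus and transplant cohort conditions. In Appendix B, treatment claims help to establish two of them: "MS-specific disease-modifying therapy fills/infusions during the 365-day baseline period" for multiple sclerosis, and, as one route for transplant, two or more "claims for ANY codes for immune-modulating or immunosuppressant therapy".

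Section 9.3.3 describes the propensity score: "These variables will include maternal age, calendar year, maternal comorbidities", followed by lifestyle factors, race/ethnicity and region, with healthcare encounters counted as well. Neither that section nor Appendix I lists an immunosuppressive medication.

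**The concern.** The criterion and the list that carries it out do not match. The criterion is about fetal risk, whereas the list is about names. Where the authors wanted several forms of one substance covered, they wrote them out. Read by the same convention, an unnamed form is not covered, and a programmer who pulls codes for leflunomide would not retrieve teriflunomide.

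This matters because the sponsor has already judged mycophenolate mofetil and leflunomide to be disqualifying. If another product delivers the same active substance, a pregnancy exposed to it is kept or dropped according to the product name on the claim. The exclusion is there to keep drug-related malformations out of the primary comparison. These pregnancies would remain in it, and matching as described would not balance them.

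**Working it through.** **1. The text, side by side.**

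| Question | What the protocol shows |
|---|---|
| Is the list open? | No. It applies to the listed drugs. Appendices G and I say their code lists may be modified, and Section 9.3.1 allows added vaccine codes. Appendix C has no such clause. |
| Are related forms written out? | Yes for valproate and phenytoin; no for mycophenolate and leflunomide. |
| Are the missing names elsewhere? | Mycophenolic acid, mycophenolate sodium and teriflunomide do not occur anywhere in the protocol. |
| Does matching deal with them? | No immunosuppressant is among the covariates named in Section 9.3.3 or Appendix I. |
| Does the outcome definition remove them? | No. Section 9.3.2.1.1 removes syndromes of known cause by pointing to Appendix D, which holds only chromosomal and genetic codes. |

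One link lies outside the documents: that the unlisted products deliver the same active substances, and that they are used in transplant, lupus and multiple sclerosis. This is general drug identity, taken here as an assumption for the sponsor to verify.

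**2. Inputs for size.** From Section 9.5: 3% background malformation prevalence, 711 exposed and 2133 unexposed infants, target ratio 2.0. At risks of 6% and 3%, a two-sided 5% test with these numbers has 92.5% power, so the planned size is sufficient. Usage shares and drug risks are not in the documents, so everything below that uses them is assumed.

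**3. No vaccine effect, 3-fold drug risk assumed.** Let a and b be the shares of exposed and unexposed pregnancies with an unlisted product. The observed ratio is (1 + 2a)/(1 + 2b).

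- a = b: 1.00.
- a = 3%, b = 1%: 1.06/1.02 = 1.04.
- a = 10%, b = 2%: 1.20/1.04 = 1.15.
- The same shares reversed: 1.02/1.06 = 0.96 and 1.04/1.20 = 0.87.

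In cases: 711 × 0.03 is about 21 expected malformations among the exposed. The excess is 711 × 0.03 × 0.06 = 1.3 cases at 3% use and 711 × 0.10 × 0.06 = 4.3 at 10%.

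**4. No vaccine effect, assumed risk r of 10% to 25% in users.** Risk in a group is (1 − share) × 0.03 + share × r.

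- 2% versus 1% use: ratio 1.02 to 1.07.
- 5% versus 2%: 1.07 to 1.19. At r = 25% this is 0.0410/0.0344.
- 5% versus 0%: 1.12 to 1.37.

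**5. True ratio 2.0, equal use f.** Assume the vaccine adds nothing to a drug user's risk. Then the ratio is [(1 − f) × 0.06 + f × r]/[(1 − f) × 0.03 + f × r].

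- f = 0.5%, r = 10%: 0.0602/0.03035 = 1.98, power 92%.
- f = 3%, r = 25%: 0.0657/0.0366 = 1.80, power 88%.

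If the vaccine instead doubled risk in drug users too, equal use would leave the ratio at 2.0.

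**The case against.** Five points can be made on the other side.

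*The key link is pharmacology that the protocol does not contain.* True, and it has to be labelled as such. It is drug identity that the sponsor can check at once, not a finding recalled from a study, and the mismatch between a broad criterion and a closed list can be seen without it.

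*Appendix C is a table of names, and code sets are commonly left to later specifications.* This has some force for mycophenolate, where a code set might be built to include the other forms. It has much less for teriflunomide, which is a different drug name. The protocol itself fixes the list and writes out related forms elsewhere in it, so silence here is not neutral.

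*The size is assumed, and the likely effect is small.* This stands. With 3% risk in both groups, the standard error of the log ratio is √(0.97/21.33 + 0.97/63.99) = 0.246, so a 95% interval around a null ratio runs from about 0.62 to 1.62. A shift to 1.04 is minor against that. The 10% versus 2% case is strained: at Table 1 midpoints, multiple sclerosis, lupus and transplant make up 0.1955/0.4705 = 42% of the listed total, so 10% overall would need about a quarter of those exposed pregnancies on an unlisted product. Multiple sclerosis alone is 0.08/0.4705 = 17%, but prevalence of the disease says nothing about use of one drug.

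*Sensitivity analyses for unobserved confounding are planned* (Sections 9.7.2.3 and 9.9.1). They limit the consequence but do not remove the pregnancies. In the descriptive fallback of Section 9.7.3 no additional analyses are done.

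*Appendix B does not contradict Appendix C.* A reader might infer a contradiction, because a treatment fill can count towards multiple sclerosis eligibility. The documents do not support that reading. The fill helps to confirm a diagnosis, at least one diagnosis claim is still required, and exclusion is a separate step.

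**Conclusion.** The concern holds as a mismatch between the exclusion criterion in Section 9.2.1 and the list that applies it. Followed as written, Appendix C would keep in the primary malformation analysis pregnancies exposed to other products of two substances that the sponsor has already excluded, given the drug-identity assumption.

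A reader might go further and infer that vaccinated women use these products more, so that the malformation ratio is pushed upward. The documents do not support this. The indication does cover immunosuppression due to therapy, but every cohort member, vaccinated or not, has a qualifying condition, and no usage figure is given. Neither the direction nor the size of any bias can be derived. Equal use gives no bias under the null and at most modest dilution of a true ratio of 2.0, and clearly unequal use is needed to move a null ratio noticeably. The ratios of 1.04 and 1.15 are illustrations under an assumed 3-fold risk, not estimates.

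This should be corrected because the list is easy to put right, not because a large distortion has been shown.

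**What to change.** State in Appendix C that each entry covers all NDC and HCPCS codes of products delivering the same active substance, as is already done by name for valproate. Change the two entries to 'Mycophenolate (mofetil, sodium, mycophenolic acid)' and 'Leflunomide and teriflunomide', once the sponsor has verified the drug identity. Check the remaining single-name entries on the same principle.

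The cost is two extended list entries and a few more excluded pregnancies. The loss of exposed pregnancies can be counted in the feasibility assessment, where the threshold is 237.

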Appendix D. Diagnosis Codes for Chromosomal or Genetic Anomalies

Live birth pregnancies among women who deliver an infant with any of following diagnoses for chromosomal or genetic anomalies will be excluded from the study population. Diagnoses will be identified in the one-year period after birth.

ICD-10-CM Diagnosis	Description
Q90.x	Down syndrome
Q91.x	Trisomy 18 and Trisomy 13
Q92.xx	Other trisomies and partial trisomies of the autosomes, not elsewhere classified
Q93.xx	Monosomies and deletions from the autosomes, not elsewhere classified
Q95.x	Balanced rearrangements and structural markers, not elsewhere classified
Q96.x	Turner's syndrome
Q97.x	Other sex chromosome abnormalities, female phenotype, not elsewhere classified
Q98.x	Other sex chromosome abnormalities, male phenotype, not elsewhere classified
Q99.x	Other chromosome abnormalities, not elsewhere classified
Q87.4xx	Marfan's syndrome
D82.1	Di George's syndrome

Appendix E. Live Birth Diagnosis and Procedure Codes

Live birth pregnancies will be identified with the following diagnosis and procedure codes as described in Section 9.2.1.1.

Code	Code Category	Description
0W8NXZZ	ICD-10-PCS	Division of Female Perineum, External Approach
10900ZC	ICD-10-PCS	Drainage of Amniotic Fluid, Therapeutic from Products of Conception, Open Approach
10903ZC	ICD-10-PCS	Drainage of Amniotic Fluid, Therapeutic from Products of Conception, Percutaneous Approach
10904ZC	ICD-10-PCS	Drainage of Amniotic Fluid, Therapeutic from Products of Conception, Percutaneous Endoscopic Approach
10907ZC	ICD-10-PCS	Drainage of Amniotic Fluid, Therapeutic from Products of Conception, Via Natural or Artificial Opening
10908ZC	ICD-10-PCS	Drainage of Amniotic Fluid, Therapeutic from Products of Conception, Via Natural or Artificial Opening Endoscopic
10D00Z0	ICD-10-PCS	Extraction of Products of Conception, Classical, Open Approach
10D00Z1	ICD-10-PCS	Extraction of Products of Conception, Low Cervical, Open Approach
10D00Z2	ICD-10-PCS	Extraction of Products of Conception, Extraperitoneal, Open Approach
10D07Z3	ICD-10-PCS	Extraction of Products of Conception, Low Forceps, Via Natural or Artificial Opening
10D07Z4	ICD-10-PCS	Extraction of Products of Conception, Mid Forceps, Via Natural or Artificial Opening
10D07Z5	ICD-10-PCS	Extraction of Products of Conception, High Forceps, Via Natural or Artificial Opening
10D07Z6	ICD-10-PCS	Extraction of Products of Conception, Vacuum, Via Natural or Artificial Opening
10D07Z7	ICD-10-PCS	Extraction of Products of Conception, Internal Version, Via Natural or Artificial Opening
10D07Z8	ICD-10-PCS	Extraction of Products of Conception, Other, Via Natural or Artificial Opening
10E0XZZ	ICD-10-PCS	Delivery of Products of Conception, External Approach
10S07ZZ	ICD-10-PCS	Reposition Products of Conception, Via Natural or Artificial Opening
O1002	ICD-10-CM	Pre-existing essential hypertension complicating childbirth
O1012	ICD-10-CM	Pre-existing hypertensive heart disease complicating childbirth
O1022	ICD-10-CM	Pre-existing hypertensive chronic kidney disease complicating childbirth
O1032	ICD-10-CM	Pre-existing hypertensive heart and chronic kidney disease complicating childbirth
O1042	ICD-10-CM	Pre-existing secondary hypertension complicating childbirth
O1092	ICD-10-CM	Unspecified pre-existing hypertension complicating childbirth
O114	ICD-10-CM	Pre-existing hypertension with pre-eclampsia, complicating childbirth
O1204	ICD-10-CM	Gestational edema, complicating childbirth
O1214	ICD-10-CM	Gestational proteinuria, complicating childbirth

Code	Code Category	Description
O1224	ICD-10-CM	Gestational edema with proteinuria, complicating childbirth
O134	ICD-10-CM	Gestational [pregnancy-induced] hypertension without significant proteinuria, complicating childbirth
O1404	ICD-10-CM	Mild to moderate pre-eclampsia, complicating childbirth
O1414	ICD-10-CM	Severe pre-eclampsia complicating childbirth
O1424	ICD-10-CM	HELLP syndrome, complicating childbirth
O1494	ICD-10-CM	Unspecified pre-eclampsia, complicating childbirth
O164	ICD-10-CM	Unspecified maternal hypertension, complicating childbirth
O2402	ICD-10-CM	Pre-existing type 1 diabetes mellitus, in childbirth
O2412	ICD-10-CM	Pre-existing type 2 diabetes mellitus, in childbirth
O2432	ICD-10-CM	Unspecified pre-existing diabetes mellitus in childbirth
O24420	ICD-10-CM	Gestational diabetes mellitus in childbirth, diet controlled
O24424	ICD-10-CM	Gestational diabetes mellitus in childbirth, insulin controlled
O24425	ICD-10-CM	Gestational diabetes mellitus in childbirth, controlled by oral hypoglycemic drugs
O24429	ICD-10-CM	Gestational diabetes mellitus in childbirth, unspecified control
O2482	ICD-10-CM	Other pre-existing diabetes mellitus in childbirth
O2492	ICD-10-CM	Unspecified diabetes mellitus in childbirth
O252	ICD-10-CM	Malnutrition in childbirth
O2662	ICD-10-CM	Liver and biliary tract disorders in childbirth
O2672	ICD-10-CM	Subluxation of symphysis (pubis) in childbirth
O6012X0	ICD-10-CM	Preterm labor second trimester with preterm delivery second trimester, not applicable or unspecified
O6012X1	ICD-10-CM	Preterm labor second trimester with preterm delivery second trimester, fetus 1
O6012X2	ICD-10-CM	Preterm labor second trimester with preterm delivery second trimester, fetus 2
O6012X3	ICD-10-CM	Preterm labor second trimester with preterm delivery second trimester, fetus 3
O6012X4	ICD-10-CM	Preterm labor second trimester with preterm delivery second trimester, fetus 4
O6012X5	ICD-10-CM	Preterm labor second trimester with preterm delivery second trimester, fetus 5
O6012X9	ICD-10-CM	Preterm labor second trimester with preterm delivery second trimester, other fetus
O6013X0	ICD-10-CM	Preterm labor second trimester with preterm delivery third trimester, not applicable or unspecified
O6013X1	ICD-10-CM	Preterm labor second trimester with preterm delivery third trimester, fetus 1
O6013X2	ICD-10-CM	Preterm labor second trimester with preterm delivery third trimester, fetus 2
O6013X3	ICD-10-CM	Preterm labor second trimester with preterm delivery third trimester, fetus 3

Code	Code Category	Description
O6013X4	ICD-10-CM	Preterm labor second trimester with preterm delivery third trimester, fetus 4
O6013X5	ICD-10-CM	Preterm labor second trimester with preterm delivery third trimester, fetus 5
O6013X9	ICD-10-CM	Preterm labor second trimester with preterm delivery third trimester, other fetus
O6014X0	ICD-10-CM	Preterm labor third trimester with preterm delivery third trimester, not applicable or unspecified
O6014X1	ICD-10-CM	Preterm labor third trimester with preterm delivery third trimester, fetus 1
O6014X2	ICD-10-CM	Preterm labor third trimester with preterm delivery third trimester, fetus 2
O6014X3	ICD-10-CM	Preterm labor third trimester with preterm delivery third trimester, fetus 3
O6014X4	ICD-10-CM	Preterm labor third trimester with preterm delivery third trimester, fetus 4
O6014X5	ICD-10-CM	Preterm labor third trimester with preterm delivery third trimester, fetus 5
O6014X9	ICD-10-CM	Preterm labor third trimester with preterm delivery third trimester, other fetus
O6022X0	ICD-10-CM	Term delivery with preterm labor, second trimester, not applicable or unspecified
O6022X1	ICD-10-CM	Term delivery with preterm labor, second trimester, fetus 1
O6022X2	ICD-10-CM	Term delivery with preterm labor, second trimester, fetus 2
O6022X3	ICD-10-CM	Term delivery with preterm labor, second trimester, fetus 3
O6022X4	ICD-10-CM	Term delivery with preterm labor, second trimester, fetus 4
O6022X5	ICD-10-CM	Term delivery with preterm labor, second trimester, fetus 5
O6022X9	ICD-10-CM	Term delivery with preterm labor, second trimester, other fetus
O6023X0	ICD-10-CM	Term delivery with preterm labor, third trimester, not applicable or unspecified
O6023X1	ICD-10-CM	Term delivery with preterm labor, third trimester, fetus 1
O6023X2	ICD-10-CM	Term delivery with preterm labor, third trimester, fetus 2
O6023X3	ICD-10-CM	Term delivery with preterm labor, third trimester, fetus 3
O6023X4	ICD-10-CM	Term delivery with preterm labor, third trimester, fetus 4
O6023X5	ICD-10-CM	Term delivery with preterm labor, third trimester, fetus 5
O6023X9	ICD-10-CM	Term delivery with preterm labor, third trimester, other fetus
O632	ICD-10-CM	Delayed delivery of second twin, triplet, etc.
O670	ICD-10-CM	Intrapartum hemorrhage with coagulation defect
O678	ICD-10-CM	Other intrapartum hemorrhage
O679	ICD-10-CM	Intrapartum hemorrhage, unspecified
O68	ICD-10-CM	Labor and delivery complicated by abnormality of fetal acid-base balance
O690XX0	ICD-10-CM	Labor and delivery complicated by prolapse of cord, not applicable or unspecified
O690XX1	ICD-10-CM	Labor and delivery complicated by prolapse of cord, fetus 1
O690XX2	ICD-10-CM	Labor and delivery complicated by prolapse of cord, fetus 2
O690XX3	ICD-10-CM	Labor and delivery complicated by prolapse of cord, fetus 3
O690XX4	ICD-10-CM	Labor and delivery complicated by prolapse of cord, fetus 4

Code	Code Category	Description
O690XX5	ICD-10-CM	Labor and delivery complicated by prolapse of cord, fetus 5
O690XX9	ICD-10-CM	Labor and delivery complicated by prolapse of cord, other fetus
O691XX0	ICD-10-CM	Labor and delivery complicated by cord around neck, with compression, not applicable or unspecified
O691XX1	ICD-10-CM	Labor and delivery complicated by cord around neck, with compression, fetus 1
O691XX2	ICD-10-CM	Labor and delivery complicated by cord around neck, with compression, fetus 2
O691XX3	ICD-10-CM	Labor and delivery complicated by cord around neck, with compression, fetus 3
O691XX4	ICD-10-CM	Labor and delivery complicated by cord around neck, with compression, fetus 4
O691XX5	ICD-10-CM	Labor and delivery complicated by cord around neck, with compression, fetus 5
O691XX9	ICD-10-CM	Labor and delivery complicated by cord around neck, with compression, other fetus
O692XX0	ICD-10-CM	Labor and delivery complicated by other cord entanglement, with compression, not applicable or unspecified
O692XX1	ICD-10-CM	Labor and delivery complicated by other cord entanglement, with compression, fetus 1
O692XX2	ICD-10-CM	Labor and delivery complicated by other cord entanglement, with compression, fetus 2
O692XX3	ICD-10-CM	Labor and delivery complicated by other cord entanglement, with compression, fetus 3
O692XX4	ICD-10-CM	Labor and delivery complicated by other cord entanglement, with compression, fetus 4
O692XX5	ICD-10-CM	Labor and delivery complicated by other cord entanglement, with compression, fetus 5
O692XX9	ICD-10-CM	Labor and delivery complicated by other cord entanglement, with compression, other fetus
O693XX0	ICD-10-CM	Labor and delivery complicated by short cord, not applicable or unspecified
O693XX1	ICD-10-CM	Labor and delivery complicated by short cord, fetus 1
O693XX2	ICD-10-CM	Labor and delivery complicated by short cord, fetus 2
O693XX3	ICD-10-CM	Labor and delivery complicated by short cord, fetus 3
O693XX4	ICD-10-CM	Labor and delivery complicated by short cord, fetus 4
O693XX5	ICD-10-CM	Labor and delivery complicated by short cord, fetus 5
O693XX9	ICD-10-CM	Labor and delivery complicated by short cord, other fetus
O694XX0	ICD-10-CM	Labor and delivery complicated by vasa previa, not applicable or unspecified
O694XX1	ICD-10-CM	Labor and delivery complicated by vasa previa, fetus 1
O694XX2	ICD-10-CM	Labor and delivery complicated by vasa previa, fetus 2
O694XX3	ICD-10-CM	Labor and delivery complicated by vasa previa, fetus 3

Code	Code Category	Description
O694XX4	ICD-10-CM	Labor and delivery complicated by vasa previa, fetus 4
O694XX5	ICD-10-CM	Labor and delivery complicated by vasa previa, fetus 5
O694XX9	ICD-10-CM	Labor and delivery complicated by vasa previa, other fetus
O695XX0	ICD-10-CM	Labor and delivery complicated by vascular lesion of cord, not applicable or unspecified
O695XX1	ICD-10-CM	Labor and delivery complicated by vascular lesion of cord, fetus 1
O695XX2	ICD-10-CM	Labor and delivery complicated by vascular lesion of cord, fetus 2
O695XX3	ICD-10-CM	Labor and delivery complicated by vascular lesion of cord, fetus 3
O695XX4	ICD-10-CM	Labor and delivery complicated by vascular lesion of cord, fetus 4
O695XX5	ICD-10-CM	Labor and delivery complicated by vascular lesion of cord, fetus 5
O695XX9	ICD-10-CM	Labor and delivery complicated by vascular lesion of cord, other fetus
O6981X0	ICD-10-CM	Labor and delivery complicated by cord around neck, without compression, not applicable or unspecified
O6981X1	ICD-10-CM	Labor and delivery complicated by cord around neck, without compression, fetus 1
O6981X2	ICD-10-CM	Labor and delivery complicated by cord around neck, without compression, fetus 2
O6981X3	ICD-10-CM	Labor and delivery complicated by cord around neck, without compression, fetus 3
O6981X4	ICD-10-CM	Labor and delivery complicated by cord around neck, without compression, fetus 4
O6981X5	ICD-10-CM	Labor and delivery complicated by cord around neck, without compression, fetus 5
O6981X9	ICD-10-CM	Labor and delivery complicated by cord around neck, without compression, other fetus
O6982X0	ICD-10-CM	Labor and delivery complicated by other cord entanglement, without compression, not applicable or unspecified
O6982X1	ICD-10-CM	Labor and delivery complicated by other cord entanglement, without compression, fetus 1
O6982X2	ICD-10-CM	Labor and delivery complicated by other cord entanglement, without compression, fetus 2
O6982X3	ICD-10-CM	Labor and delivery complicated by other cord entanglement, without compression, fetus 3
O6982X4	ICD-10-CM	Labor and delivery complicated by other cord entanglement, without compression, fetus 4
O6982X5	ICD-10-CM	Labor and delivery complicated by other cord entanglement, without compression, fetus 5
O6982X9	ICD-10-CM	Labor and delivery complicated by other cord entanglement, without compression, other fetus
O6989X0	ICD-10-CM	Labor and delivery complicated by other cord complications, not applicable or unspecified
O6989X1	ICD-10-CM	Labor and delivery complicated by other cord complications, fetus 1

Code	Code Category	Description	
O6989X2	ICD-10-CM	Labor and delivery complicated by other cord complications, fetus 2	
O6989X3	ICD-10-CM	Labor and delivery complicated by other cord complications, fetus 3	
O6989X4	ICD-10-CM	Labor and delivery complicated by other cord complications, fetus 4	
O6989X5	ICD-10-CM	Labor and delivery complicated by other cord complications, fetus 5	
O6989X9	ICD-10-CM	Labor and delivery complicated by other cord complications, other fetus	
O699XX0	ICD-10-CM	Labor and delivery complicated by cord complication, unspecified, not applicable or unspecified	
O699XX1	ICD-10-CM	Labor and delivery complicated by cord complication, unspecified, fetus 1	
O699XX2	ICD-10-CM	Labor and delivery complicated by cord complication, unspecified, fetus 2	
O699XX3	ICD-10-CM	Labor and delivery complicated by cord complication, unspecified, fetus 3	
O699XX4	ICD-10-CM	Labor and delivery complicated by cord complication, unspecified, fetus 4	
O699XX5	ICD-10-CM	Labor and delivery complicated by cord complication, unspecified, fetus 5	
O699XX9	ICD-10-CM	Labor and delivery complicated by cord complication, unspecified, other fetus	
O700	ICD-10-CM	First degree perineal laceration during delivery	
O701	ICD-10-CM	Second degree perineal laceration during delivery	
O7020	ICD-10-CM	Third degree perineal laceration during delivery, unspecified	
O7021	ICD-10-CM	Third degree perineal laceration during delivery, Illa	
O7022	ICD-10-CM	Third degree perineal laceration during delivery, IIIb	
O7023	ICD-10-CM	Third degree perineal laceration during delivery, IIIc	
O703	ICD-10-CM	Fourth degree perineal laceration during delivery	
O704	ICD-10-CM	Anal sphincter tear complicating delivery, not associated with third degree laceration	
O709	ICD-10-CM	Perineal laceration during delivery, unspecified	
O740	ICD-10-CM	Aspiration pneumonitis due to anesthesia during labor and delivery	
O741	ICD-10-CM	Other pulmonary complications of anesthesia during labor and delivery	
O742	ICD-10-CM	Cardiac complications of anesthesia during labor and delivery	
O743	ICD-10-CM	Central nervous system complications of anesthesia during labor and delivery	
O744	ICD-10-CM	Toxic reaction to local anesthesia during labor and delivery	
O745	ICD-10-CM	Spinal and epidural anesthesia-induced headache during labor and delivery	
O746	ICD-10-CM	Other complications of spinal and epidural anesthesia during labor and delivery	
O747	ICD-10-CM	Failed or difficult intubation for anesthesia during labor and delivery	
O748	ICD-10-CM	Other complications of anesthesia during labor and delivery	
O749	ICD-10-CM	Complication of anesthesia during labor and delivery, unspecified	
O750	ICD-10-CM	Maternal distress during labor and delivery	
O751	ICD-10-CM	Shock during or following labor and delivery	
O755	ICD-10-CM	Delayed delivery after artificial rupture of membranes	
O7581	ICD-10-CM	Maternal exhaustion complicating labor and delivery	

Code	Code Category	Description
O7582	ICD-10-CM	Onset (spontaneous) of labor after 37 completed weeks of gestation but before 39 completed weeks gestation, with delivery by (planned) cesarean section
O7589	ICD-10-CM	Other specified complications of labor and delivery
O759	ICD-10-CM	Complication of labor and delivery, unspecified
O76	ICD-10-CM	Abnormality in fetal heart rate and rhythm complicating labor and delivery
O770	ICD-10-CM	Labor and delivery complicated by meconium in amniotic fluid
O778	ICD-10-CM	Labor and delivery complicated by other evidence of fetal stress
O779	ICD-10-CM	Labor and delivery complicated by fetal stress, unspecified
O80	ICD-10-CM	Encounter for full-term uncomplicated delivery
O82	ICD-10-CM	Encounter for cesarean delivery without indication
O8802	ICD-10-CM	Air embolism in childbirth
O8812	ICD-10-CM	Amniotic fluid embolism in childbirth
O8822	ICD-10-CM	Thromboembolism in childbirth
O8832	ICD-10-CM	Pyemic and septic embolism in childbirth
O8882	ICD-10-CM	Other embolism in childbirth
O9802	ICD-10-CM	Tuberculosis complicating childbirth
O9812	ICD-10-CM	Syphilis complicating childbirth
O9822	ICD-10-CM	Gonorrhea complicating childbirth
O9832	ICD-10-CM	Other infections with a predominantly sexual mode of transmission complicating childbirth
